UNIVERSITY OF SAO PAULO
SCHOOL OF MEDICINE OF RIBEIRAO PRETO

[name]

Randomized, placebo-controlled study of corticosteroid therapy for persistent interstitial disease post-COVID-19.

Ribeirao Preto

2021

Abstract

Introduction: The new coronavirus (SARS-CoV-2) is a virus with an intense capacity for dissemination and high mortality rate. The main cause of death is viral pneumonia, characterized as organizing pneumonia that responds to treatment with corticosteroids. After 1 month of the acute phase, 25% of patients have complete recovery from lung lesions. However, lung lesions can evolve as persistent interstitial lung disease; it is possible that this persistent disease is also responsive to corticosteroid therapy. There are no controlled and randomized studies on any treatment and its effect on the natural history of this subacute or late manifestation of COVID-19.

Objective: To understand the effect of oral corticosteroid therapy in the treatment of persistent pulmonary manifestations (clinical and radiological) in patients who had moderate, severe, and critical forms of COVID-19. To understand the role of some risk factors in the development of this form of lung disease. To add information on the natural history of interstitial lung disease secondary to SARS-CoV-2 pulmonary infection.

Methodology: Randomized, double-blind, placebo-controlled study of patients who had COVID-19 viral pneumonia. Patients included after 12 weeks of COVID-19 diagnosis with RT-PCR or imaging tests that confirm the infection for inclusion in the protocol 100 patients with changes in high-resolution chest tomography and diffusion spirometry, will be divided into two groups, placebo and treatment; the treatment group will receive prednisolone at a dose of 0.5 mg/kg/day for 1 month and weaning in 30 days. Clinical, laboratory, functional, and imaging evaluations will be performed at the beginning, after 3 and 6 months of treatment and monthly telephone calls.

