A study on the use of corticosteroids in patients with pulmonary sequelae showed significant improvement after the use of a dose of 0.5 mg/kg, but with rapid weaning and weaning beginning in the first week of use. This study did not have a control group, and patients were followed for 3 months only after inclusion and initiation of treatment (MYALL et al., 2021). The use of corticosteroids plays a crucial role in the treatment of inflammatory lung disease related to COVID-19, apparently in all phases of the disease.

Since COVID-19-related lung lesions in the acute phase are responsive to corticosteroid therapy, it is inferred that, for persistent interstitial lung disease that demonstrates an inflammatory pattern with alveolar involvement, corticosteroid therapy may also have an important role. There are no controlled and randomized studies on any treatment and its effect on the natural history of this complication of COVID-19.

Objective

To understand the effect of oral corticosteroid therapy in patients who had moderate to severe forms of coronavirus to treat persistent pulmonary manifestations with a radiological pattern of interstitial disease.

To understand the role of some risk factors for the development of pulmonary fibrosis in patients who had pulmonary infection by coronavirus with persistent interstitial disease.

To add information on the natural history of lung disease in patients who had moderate to severe forms of COVID-19.

Methodology

The study will be conducted at the Hospital das Clínicas of the Ribeirão Preto School of Medicine of the University of São Paulo. It will be a randomized, double-blind, placebo-controlled study of patients who had pneumonia caused by the novel coronavirus and were treated as outpatients, hospitalized, or who required oxygen therapy or orotracheal intubation.

Treatment: corticosteroid therapy with prednisolone at a dose of half a milligram per kilogram per day, lasting 1 month, which will be gradually withdrawn with a 50% reduction in the dose every 7 days, up to a minimum dose of 5 mg for 7 days before stopping completely. The placebo group will receive tablets identical to prednisolone 20 mg for 1 month, and then the reduction will be done with placebo tablets identical to the 20 mg and 5 mg tablets.

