The identification of the bottles and the preparation of the placebo tablets will be carried out by a compounding pharmacy that will identify the labels by codes, and a researcher on the team will learn the content related to each code (placebo or prednisolone). This researcher will not have access to the study care or procedures.

Patients who received placebo took a similar number of tablets for similar time span.

Visits/Protocol: After 12 to 20 weeks of the diagnosis of pneumonia caused by the new coronavirus patients will be a standardized time. A medical evaluation, laboratory, imaging, and functional tests will be carried out with a view to immediate entry into the study. This will be considered the first visit. Patients will be randomized, and treatment will be given on the first visit. The evaluations will be carried out on this first visit (baseline) and will be repeated after 3 and 6 months from the first visit. The recruitment period will be 12 months, and the follow-up period for each patient will be 9 months. Depending on the study outcomes and the interest of the research team, this follow-up may be extended through a new research project.

In addition to quarterly assessments, these patients will be assisted with monthly telephone calls to check adherence and possible adverse effects.

If any patient is still using corticosteroid therapy, they will also be randomized and will be instructed to wean off the corticosteroid in use within 15 days and will receive the study treatment while reducing the dose of the previous corticosteroid until it is completely removed.

Randomization

Numbers 1 to 100 were randomly mixed up using a computer randomizer program. The first fifty were allocated as placebo and the last fifty as Treatment. Included patients received a number consecutively from 1 to 100. Only one researcher ([name]) knew to which group every number (patient) belonged, placebo or Treatment. This researcher labeled medicine vials accordingly.

Patients

One hundred patients will be included in the study, of which 50 will be in the control group and 50 in the treatment group.

Inclusion criteria:

- Over 18 years of age;
- Diagnosis of COVID-19 by RT-PCR (Reverse transcription polymerase chain reaction), a test that detects the presence of viral antigen in nasal and oropharyngeal secretions or chest tomography typical of COVID-19 according to radiological standardization for COVID-19 cases (Machnicki, 2021);

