- level of urea, LDH, and D-dimers at hospital admission;
- History of smoking;
- History of alcoholism;
- Symptoms persisting after hospital discharge secondary to COVID-19 infection: chronic cough, dyspnea on exertion (dyspnea classification by MRC - appendix 2), chest pain, chronic fatigue, and joint pain.

Follow-up telephone calls will be made monthly to increase adherence and check for possible adverse effects of corticosteroid use.

Ethical aspects

The project will be submitted for review by the Research Ethics Committee of the Hospital das Clínicas de Ribeirão Preto through the Plataforma Brasil. Information about the objectives, procedures, risks, and benefits of the study will be passed on to patients, and upon their agreement to participate, they will be invited to sign an informed consent form (ICF).

Statistical analysis

ANOVA was used to assess continuous variables (FEV1 liter, FEV1%, FVC liter, FVC%, TLC liter, TLC%, DLCO, MIP, MEP, 6MWT distance, ESR, CRP, D-dimer).

SF-36 scores were analyzed using a negative binomial regression model with repeated measures and a logarithmic link function, given that we can consider these outcomes as discrete and non-continuous quantitative variables. This model was used because the assumptions of normality and homoscedasticity of residues for the ANOVA analysis were not valid. From the model estimates, the relative increase (or

reduction) in the mean was calculated based on the expression $AR(\beta) = [\exp(\beta) - 1]*100\%.$

MRC dyspnea score and PCFS scale are ordinal categorical variables; the analysis used an ordinal multinomial regression mode, which estimates the odds ratio of higher "scores", meaning worse.

The analysis of the dichotomized PCFS used a log-binomial regression model, which estimates the prevalence ratio of grade 3 or 4 occurring between groups and times.

Reference

BORG G. Psychophysical scaling with applications in physical work and the perception of exertion. **Scand J Work Environ Health**. 1990 16 Suppl 155-8. doi: 10.5271/sjweh.1815. PubMed ID: 2345867

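### Monthly calls are too sparse for a course of about two months: the first adherence and adverse-effect check after baseline comes at about the end of the full-dose month

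*Combined protocol and SAP*

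**What the plan says.** Treatment is handed out at the first visit. The Treatment paragraph of the Methodology describes "prednisolone at a dose of half a milligram per kilogram per day, lasting 1 month". After that month the drug is to be "gradually withdrawn with a 50% reduction in the dose every 7 days". The same paragraph sets the end of the taper as follows: "up to a minimum dose of 5 mg for 7 days before stopping completely". The Abstract describes the course as "prednisolone at a dose of 0.5 mg/kg/day for 1 month and weaning in 30 days" and gives no dose steps for the wean.

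Evaluations take place at baseline and "will be repeated after 3 and 6 months from the first visit" (Visits/Protocol). Between them the stated contact is by telephone. Visits/Protocol gives its purpose: "these patients will be assisted with monthly telephone calls to check adherence and possible adverse effects". The section on medical evaluation and laboratory tests adds: "Follow-up telephone calls will be made monthly to increase adherence and check for possible adverse effects of corticosteroid use".

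Neither place gives the day of the first call, the total number of calls, or any link between call dates and dosing. The protocol text describes no pill count, diary, bottle return or earlier contact.

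**The concern.** A monthly rhythm suits a treatment that lasts many months. This one lasts about two, and most of the drug is given in the first. A first call at one month reaches the patient when the full-dose phase is over or about to end. A call cannot raise adherence to tablets that were already due and missed.

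Two things are at stake:

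- **Adherence.** A patient who stops early is found after most of the planned exposure has passed. With 50 patients per arm, uncorrected early stopping would dilute the contrast between prednisolone and placebo.
- **Adverse effects.** Events during the full-dose month are reported from memory, up to a month later. The exclusion criteria show that the protocol takes steroid risk seriously: they name uncontrolled diabetes, untreated glaucoma, current infection and untreated psychiatric disorders. Visits/Protocol also admits patients still on a corticosteroid, who wean off it within 15 days while taking study treatment. That overlap is over before a call at about day 30.

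**Working it through.** **Inputs from the documents:** full dose 0.5 mg/kg/day for 1 month; halving every 7 days, ending with 5 mg for 7 days (Methodology); a 30-day wean (Abstract); drug from visit 1; visits at months 3 and 6; monthly calls; tablets of 20 mg and 5 mg.

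**Assumptions:** a month is 30 days; the first call is on day 30 and the second on day 60; body weight is 40-160 kg (the documents give no weights). The Methodology rule is read as halving while the dose stays above 5 mg, then 5 mg for 7 days.

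**Step 1. The plan's own figure.** The Abstract's 30-day wean is not reproduced by the Methodology rule. Over the assumed weights the rule gives a taper of 14 days (40 kg), 21 days (above 40 to 80 kg) or 28 days (above 80 to 160 kg). The course is then 44, 51 or 58 days, against about 60 in the Abstract.

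**Step 2. Share of drug taken by day 30, Methodology rule.** With D = 0.5 × weight, share = 30D / (30D + taper mg).

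| Weight | D (mg) | Taper steps, 7 days each (mg) | Last dose | Total mg | Share by day 30 |
|---|---|---|---|---|---|
| 40 kg | 20 | 10, 5 | day 44 | 600 + 105 = 705 | 85.1% |
| 60 kg | 30 | 15, 7.5, 5 | day 51 | 900 + 192.5 = 1,092.5 | 82.4% |
| 80 kg | 40 | 20, 10, 5 | day 51 | 1,200 + 245 = 1,445 | 83.0% |
| 90 kg | 45 | 22.5, 11.25, 5.625, 5 | day 58 | 1,350 + 310.6 = 1,660.6 | 81.3% |
| 160 kg | 80 | 40, 20, 10, 5 | day 58 | 2,400 + 525 = 2,925 | 82.1% |

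Over the weights tried, exact doses give 81.3-85.1%. Rounding doses to 5 mg gives 77.8-85.1%. The low end is 90 kg with steps of 25, 15, 10 and 5 mg: 1,350 / (1,350 + 385) = 77.8%.

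**Step 3. The same share under the Abstract (60 days, 40-120 kg).** The steps must be assumed:

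- Linear decline to 5 mg: 62-66%. For example, at 40 kg, 600 / (600 + 367.5) = 62.0%.
- Equal-length halving steps: 73-81%. At 40 kg, 600 / (600 + 225) = 72.7%.
- Seven-day halving steps, with 5 mg held to day 60: 76-81%. At 40 kg, 600 / (600 + 185) = 76.4%.

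**Step 4. Sensitivity to the calendar, Methodology rule.** Taking the month as 28 or 31 days, with the call on its last day, gives 76.6-85.5% across exact and rounded doses. A call on day 28 of a 30-day full-dose month gives 72.6-79.4%.

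**Step 5. Where later contacts fall.**

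- A day-60 call is 16, 9 or 2 days after the last dose under the Methodology, and on the last dosing day under the Abstract.
- With calls every 28 days, the second (day 56) comes 2 days before the end of a 58-day course and 4 days before the end of a 60-day course. It comes after the end of a 44- or 51-day course.
- The month 3 visit (day 90) is at least 90 − 58 = 32 days after the last dose under the Methodology, and about 30 days after it under the Abstract.
- Calls after month 3 therefore fall after dosing on every schedule tried.

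**The case against.** The strongest reply is that monthly calls are a legitimate choice of frequency, and that the dose share rests on call days and body weights the documents do not give. Cumulative dose is also the measure that makes the gap look widest. By time on treatment, day 30 is 50-68% of the course (30/60 to 30/44). All of this is fair, and it is why ranges are given. It does not supply a contact inside the full-dose month.

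Three stronger readings are tempting, and the documents do not support them:

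- A reader might infer that more than 80% of the drug is always taken before the first call. That holds only for the Methodology taper with exact doses and a call at the end of the full-dose month. It cannot be attached to the Abstract's 60-day course.
- A reader might infer that every call after the first comes after the last dose. The second call can fall on or just before the last dosing day. Above 160 kg the halving rule adds another 7-day step, so at 170 kg the course runs to day 65.
- A reader might infer that harms in the full-dose month escape every scheduled contact. The first call can still capture them by recall.

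It can also be said that the adherence to be increased might mean adherence to follow-up, and that late calls can record persisting effects and help retention. The wording allows this, so the later calls are not pointless. But the same sentence refers to effects of corticosteroid use, so checking the drug course is at least part of their purpose.

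Finally, randomization and analysis are described in the past tense, so some calls may already have been made. The documents do not settle this.

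**Conclusion.** The concern holds as a mismatch of timing. On any schedule tried, well over half of the cumulative dose precedes a first call at about day 30: about 78-85% under the Methodology and about 62-81% under the Abstract. At most one further call falls within dosing, and then only in its last days, for weights up to 160 kg. The checks are delayed and depend on recall, but they do exist.

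The effect on the treatment comparison cannot be sized, because the documents give no non-adherence rate or target effect. This is an inexpensive improvement to conduct and safety recording, and it does not by itself undermine the trial's results.

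**What to change.** In Visits/Protocol and in the section on medical evaluation and laboratory tests, replace the bare monthly rhythm with call days counted from the first dose. Keep the month 1 and month 2 calls. Add one call near the middle of the full-dose month and one during the taper. Use the same adherence and adverse-effect questions at every call in both arms.

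There are two ways to provide the extra calls:

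- **Move calls planned after month 3.** If calls fall only between visits, these are months 4 and 5; the total number of calls should be stated. This adds no workload but leaves less contact between months 3 and 6, which may slightly affect retention.
- **Keep the later calls and add two.** This costs two short calls per patient.

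Neither option changes a dose or a clinical rule. Before the taper call is dated, the sponsor must reconcile the Abstract's 30-day wean with the Methodology's halving rule, which gives 14 to 28 days over the assumed weights. If calls have already been made, report the days on which they took place and what was asked.

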In another study, in patients who required mechanical ventilation, follow-up after 3 months showed complete recovery of lung lesions in only 2 of the 41 patients evaluated. In this study, 89% of patients still had ground-glass opacities according to computed tomography (CT), signs of reticulation and fibrotic bands, with and without parenchymal distortion, bronchiectasis and bronchiolectasis in up to 67% of cases, presence of emphysematous destruction or cavities, with worsening and of pre-existing emphysema. Some patients presented areas of air retention, but this was not a frequent finding, and traction bronchiectasis was rare. This study showed that pulmonary sequelae in patients who had extensive lung involvement are very common and can progress to permanent interstitial lung disease. Also, most people who required mechanical ventilation had changes in lung function and residual changes visualized on high-resolution CT (HRCT) (VAN GASSEL et al., 2021).

The evaluation after 6 months of hospital discharge of patients with COVID-19 showed persistent pulmonary changes on CT in 52% of individuals who did not require oxygen support and 54% of those who required mechanical ventilation,

noninvasive ventilation, or other ventilatory support. Regarding DLCO, even patients with the mild form of the disease may maintain alterations, present in 22% of patients who did not require oxygen therapy and in 56% of patients who required some type of ventilatory support (HUANG et al., 2021).

The treatment of the pulmonary condition still in the acute phase in patients requiring orotracheal intubation and oxygen therapy (DE BACKER; AZOULAY; VINCENT, 2020) demonstrated benefit with immunosuppressive doses of corticosteroid therapy due to a pattern of injury to the lung tissue with lymphocytic alveolitis, acute fibrinoid injury and organizing pneumonia (REMMELINK et al., 2020), all of which are acute alterations responsive to corticosteroid therapy.

In hospitalized patients, the use of corticosteroid therapy with dexamethasone and methylprednisolone has the potential to reduce mortality. Furthermore, the comparison between the two types of corticosteroids showed that the use of methylprednisolone was more effective (KO et al., 2021).

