All questionnaires will be applied by the doctor responsible for the project, will be applied during the clinical evaluation, and will be part of the patient's anamnesis; the data obtained will be included in the medical record.

4 - MEDICAL EVALUATION AND LABORATORY TESTS

The medical evaluation includes anamnesis, clinical examination (clinical pulmonary and cardiac examination and general clinical examination, including weight and height measurements), and measurement of vital signs (heart rate, respiratory rate, oxygen saturation by pulse oximetry, blood pressure). The medical evaluation aims to identify changes in pulmonary auscultation and signs of chronic respiratory disease, in addition to evaluating other pathologies that may be grounds for exclusion from the research project, such as heart failure, pulmonary embolism, recent heart attack, inability to perform the proposed tests, such as neuropathy in critically ill patients.

Laboratory tests will be included to check for possible persistent inflammatory activity of the coronavirus in the body since there is still inflammatory lung disease. These tests include inflammatory markers, which are measurements of D-dimers, blood count, C-reactive protein, LDH, and erythrocyte sedimentation rate (ESR).

Some lung alterations may be pre-existing and secondary to pre-existing autoimmune diseases. Autoimmunity markers will be performed for differential diagnosis of autoimmune lung diseases: antinuclear factor (ANA) and rheumatoid factor (RF). If it is confirmed that these patients have interstitial lung disease associated with autoimmunity and overlapping with a disease secondary to SARS-CoV-2, these patients will be analyzed separately at the end of data collection.

The requested tests are part of the evaluation of patients who were hospitalized with a diagnosis of COVID-19 pneumonia and are included in the post-discharge reassessment routine.

A review of medical records to collect medical history and data on severity characteristics during hospitalization is necessary to obtain correlation data between this information and interstitial lung disease. The following variables will be evaluated to verify this correlation:

- sex, age, body mass index, previous diagnosis or during hospitalization of diabetes, systemic arterial hypertension;
- survey of intubation time and length of stay in the ICU bed;

- The extent of pulmonary involvement seen on tomography or chest X-ray at admission;

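### Acute severity is linked to diffusion in the protocol and recorded for each patient, yet the ANOVA of the continuous outcomes does not adjust for it: some precision is lost and a large chance imbalance has no prespecified remedy

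*Combined protocol and SAP*

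**What the plan says.** Methodology takes patients who had "pneumonia caused by the novel coronavirus and were treated as outpatients, hospitalized, or who required oxygen therapy or orotracheal intubation". The abstract confines this to moderate, severe and critical forms.

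Randomization describes a single list: "Numbers 1 to 100 were randomly mixed up using a computer randomizer program", and then "The first fifty were allocated as placebo and the last fifty as Treatment". No strata or blocks are mentioned. The target is 50 patients per arm.

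The Introduction treats acute severity as prognostic for the lung. It lists severity, ICU stay and intubation time among the risk factors for persistent disease, and says that diffusion changes grow with severity. It reports altered DLCO six months after discharge as "present in 22% of patients who did not require oxygen therapy and in 56% of patients who required some type of ventilatory support".

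Section 4 (Medical evaluation and laboratory tests) says: "A review of medical records to collect medical history and data on severity characteristics during hospitalization is necessary to obtain correlation data". Intubation time and length of ICU stay are on the list. The stated purpose is to relate them to interstitial disease; adjusting the treatment comparison is not mentioned.

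Statistical analysis assigns ANOVA to the continuous outcomes, DLCO among them. It names neither severity nor the baseline value as a covariate.

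**The concern.** When a variable predicts the outcome and is already being recorded, leaving it out of the treatment model puts its variation into the error term. Intervals are then wider than they need to be in a trial with 50 patients per arm.

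The second cost concerns the one allocation that is actually realised. If the arms differ markedly in the share of ventilated patients, the plan contains no model that corrects for it. An adjustment chosen after the imbalance has been seen is open to the charge that it was picked for its result. Naming the covariate beforehand removes that difficulty.

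**Working it through.** **No planned figure to reproduce.** The sample size of 100 is stated without a derivation, and no alpha, power, effect size or primary endpoint is given. Two-sided 5% and 80% power are assumed below.

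**Inputs.** From the documents: 50 per arm on a fixed 50:50 list (Randomization, Patients); DLCO abnormal in 22% against 56%, and CT abnormal in 52% against 54%, both at six months and from the same cited cohort (Introduction). Assumed: a ventilated share p of 20% to 50%, which the documents do not give, and severity treated as two groups.

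**Chance imbalance.** The number ventilated in one arm is hypergeometric (100 patients, 100p ventilated, 50 drawn). The SD of the arm difference in share is (2/50) × √[50·p(1−p)·50/99]. At p = 0.5 this is 0.04 × √6.313 = 0.1005; at p = 0.2 it is 0.04 × √4.040 = 0.0804.

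**Variance explained.** R² = p(1−p)(0.56 − 0.22)² / [m(1−m)], with m = 0.22(1−p) + 0.56p.
- p = 0.2: m = 0.288, so R² = 0.16 × 0.1156 / 0.2051 = 0.090.
- p = 0.5: m = 0.39, so R² = 0.25 × 0.1156 / 0.2379 = 0.121.

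The equivalent sample size after adjustment is 100/(1 − R²).

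| Ventilated share | SD of arm difference (points) | P(≥10 points) | P(≥20 points) | R², abnormal DLCO | Equivalent N |
|---|---|---|---|---|---|
| 20% | 8.0 | 21% | 2.3% | 9.0% | 110 |
| 30% | 9.2 | 28% | 4.9% | 11.1% | 113 |
| 40% | 9.8 | 31% | 6.6% | 12.1% | 114 |
| 50% | 10.1 | 32% | 7.1% | 12.1% | 114 |

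**Shift in the estimate.** An imbalance of 10 points moves the difference in abnormal DLCO by 10 × 0.34 = 3.4 points; 20 points moves it by 6.8. The difference needed for significance is 1.96 × √[2m(1−m)/50], or 17.8 points at p = 0.2 and 19.1 at p = 0.5.

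**CT for comparison.** With 52% against 54%, a 20-point imbalance shifts the difference by 20 × 0.02 = 0.4 points, and R² is 0.03% to 0.04%.

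**Type I error.** This was simulated with 30,000 trials per setting, at shares of 30% and 50%, using the 22%/56% contrast and also continuous outcomes with R² of 0.1 and 0.3. The unadjusted test rejects in 5.0% to 5.2% of null trials overall. Among trials with an imbalance of 20 points or more, it rejects in about 10% to 11% (22%/56% contrast, or R² = 0.1). Adjustment brings this back to about 5%.

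**Power.** Fifty per arm detects (1.96 + 0.84) × √(2/50) = 0.56 SD with 80% power. Replacing the SD by SD × √(1 − R²) gives 84% at R² = 0.10, 88% at 0.20 and 92% at 0.30. The first value is close to the binary DLCO figures; the other two only show the range, since the documents give no R² for continuous DLCO.

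**The case against.** The strongest reply is that unstratified 1:1 randomization with an unadjusted analysis is a legitimate choice. That stands. A reader might infer that a chance imbalance in severity could be mistaken for a drug effect. As a general statement this is not supported: the standard error already allows for chance imbalance, and overall type I error stays near 5%. Only imbalances of 20 points or more raise the conditional rate noticeably, and they occur in 2% to 7% of allocations.

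A reader might also infer that recovery depends strongly on acute severity. The documents do not show this. The 22% and 56% are prevalences at one time point, not recovery rates, and the same cohort shows almost no CT gradient. The Introduction lists severity beside age, LDH, smoking and other factors without ranking them.

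The contrast also comes from survivors in general. This trial requires persistent HRCT disease and DLCO at or below 80% of predicted, which narrows the range. The 9% to 12% is not conditional on baseline DLCO, and it concerns a binary outcome although the plan analyses DLCO as continuous. No figure is given for patients who needed oxygen only. These points stand and limit the size of the gain.

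The entry window ("After 12 to 20 weeks of the diagnosis of pneumonia caused by the new coronavirus") might look like a second omitted factor. No figure shows recovery changing within it, and the Introduction calls the natural recovery period uncertain. If entry were uniform over the eight weeks, the 95% range of the arm difference in mean entry time would be ±1.96 × (8/√12) × √(2/50) = ±0.9 week. There is no basis for requiring it in the model.

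**Conclusion.** The point holds as a matter of precision and prespecification, not of validity. The protocol describes severity as prognostic for diffusion and collects intubation time and ICU stay, but leaves them out of the comparison of the continuous outcomes. If the 22%/56% contrast carried over in full, adjustment would be worth about 10 to 14 extra patients in a trial of 100. The real gain is probably smaller, because of the entry criteria and because baseline DLCO takes up part of it. The insurance against a large imbalance is worth having because it costs so little.

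This rests on an assumed ventilated share of 20% to 50%, on two severity groups, and on the 22%/56% contrast as an upper guide. It applies to DLCO above all; the CT figures give no support for a similar gain on imaging. Stratifying the list is not pressed, because allocation is described in the past tense and is probably complete.

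**What to change.** In Statistical analysis, if the analysis is still open, state that the treatment comparison of the continuous outcomes, DLCO above all, includes two fixed covariates: acute-phase ventilatory support (yes/no) and the outcome's own baseline value. Report the unadjusted result alongside.

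Derive ventilatory support from the intubation and ICU items of the record review, with outpatients coded no. Write the coding rule down before the arms are compared, because oxygen therapy and noninvasive ventilation are not listed items in that review. The ordinal and log-binomial models can stay as they are.

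If the analysis has already been done, which its past tense leaves possible, the adjusted result can still be shown but should be labelled post hoc.

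The cost is one degree of freedom for severity and one for the baseline value, plus the derivation of one yes/no variable from records already under review. No extra visits or patients are needed. The gain beyond baseline adjustment alone is probably modest.
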